8.2.6. Safety Monitoring

The Lilly CP or CRP/scientist will monitor safety data throughout the course of the study. This will include monitoring and recording of all AEs, including all National Cancer Institute Common Terminology Criteria for Adverse Events (CTCAE) version 5.0 grades and SAEs.

The sponsor will review SAEs within time frames mandated by company procedures. The sponsor CP or CRP will periodically review the following data:

- trends in safety data
- laboratory analytes including proteinuria, reduced red blood cells, and decreased neutrophil count
- AEs, including monitoring of AESIs; see Section 8.3.6

When appropriate, the sponsor CP or CRP will consult with the functionally independent Global Patient Safety therapeutic area physician or clinical research scientist.

8.2.6.1. Hypersensitivity Reactions

In the event of a suspected systemic allergic/hypersensitivity reaction, additional safety data should be collected using the Infusion-related reaction/Hypersensitivity/Anaphylaxis follow-up form or documented via the eCRF.

- Hypersensitivity/Infusion-Related Reactions eCRFs are used to capture additional characteristics of the hypersensitivity/anaphylaxis/injection-related reaction that cannot be captured on the AE eCRF.
- Each symptom of the event (for example, mucocutaneous, cardiovascular, GI, CNS, other) should be assessed.

- If any of the above symptoms are observed during the assessment, a single generalized AE record should be entered on the AE eCRF (do not include symptoms in AE Term/description).
- Timing of the event occurrence is important. The investigator should indicate the timing category that is appropriate.

8.3. Adverse Events and Serious Adverse Events

The definitions of AEs and SAEs are provided in [Appendix 3](#) (Section 10.3). The investigator will use CTCAE version 5.0 (NCI 2018) to assign AE severity grades.

Adverse events will be reported by the participant (or, when appropriate, by a caregiver, surrogate, or the participant's legally authorized representative).

The investigator and any qualified designees are responsible for detecting, documenting, and recording events that meet the definition of an AE or SAE and remain responsible for following up AEs that are serious, considered related to the study intervention or study procedures, or that caused the participant to discontinue the study (see Section 7).

Investigators are responsible for monitoring the safety of participants who have entered this study and for alerting the sponsor or its designee to any event that seems unusual, even if this event may be considered an unanticipated benefit to the participant.

The investigator is responsible for the appropriate medical care of participants during the study.

8.3.1. Time Period and Frequency for Collecting AE and SAE Information

All SAEs will be collected from the signing of the ICF until participation in the study has ended.

All AEs will be collected from the signing of the ICF until participation in study has ended.

Adverse events that begin before the start of study intervention, but after signing of the ICF, will be recorded on the AE CRF.

Although all AEs after signing the ICF are recorded by the site in the CRF/electronic data entry, SAE reporting to sponsor begins after the participant has signed the ICF and has received the study intervention. However, if an SAE occurs after signing the ICF, but prior to receiving ramucirumab, it needs to be reported ONLY if it is considered reasonably possibly related to study procedures.

All SAEs will be recorded and reported to the sponsor or designee immediately, and under no circumstance should this exceed 24 hours, as indicated in [Appendix 3](#) (Section 10.3). The investigator will submit any updated SAE data to the sponsor within 24 hours of it being available.

Investigators are not obligated to actively seek AEs or SAEs after conclusion of the study participation. However, if the investigator learns of any SAE, including a death, at any time after a participant has been discharged from the study, and he/she considers the event to be reasonably related to the study intervention or study participation, the investigator must promptly notify the sponsor.

8.3.2. Method of Detecting AEs and SAEs

The method of recording, evaluating, and assessing causality of AEs and SAEs and the procedures for completing and transmitting SAE reports are provided in [Appendix 3](#) (Section 10.3).

Care will be taken not to introduce bias when detecting AEs and/or SAEs. Open-ended and nonleading verbal questioning of the participant is the preferred method to inquire about AE occurrences.

8.3.3. Follow-Up of AEs and SAEs

After the initial AE/SAE report, the investigator is required to proactively follow each participant at subsequent visits/contacts. All SAEs and AESIs (as defined in Section 8.3.6) will be followed until resolution, stabilization, the event is otherwise explained, or the participant is lost to follow-up (as defined in Section 7.3). Further information on follow-up procedures is provided in [Appendix 3](#) (Section 10.3).

8.3.4. Regulatory Reporting Requirements for SAEs

- Prompt notification by the investigator to the sponsor of an SAE is essential so that legal obligations and ethical responsibilities towards the safety of participants and the safety of a study intervention under clinical investigation are met.
- The sponsor has a legal responsibility to notify both the local regulatory authority and other regulatory agencies about the safety of a study intervention under clinical investigation. The sponsor will comply with country-specific regulatory requirements relating to safety reporting to the regulatory authority, IRB/IEC, and investigators.
- An investigator who receives an investigator safety report describing an SAE or other specific safety information (for example, summary or listing of SAEs) from the sponsor will review and then file it along with the IB and will notify the IRB/IEC, if appropriate according to local requirements.

8.3.5. Pregnancy

- Details of all pregnancies in female participants and, if indicated, female partners of male participants, will be collected after the start of study intervention and until at least 12 weeks after the last dose.
- If a pregnancy is reported, the investigator should inform the sponsor within 24 hours of learning of the pregnancy and should follow the procedures outlined in [Appendix 4](#) (Section 10.4).
- Abnormal pregnancy outcomes (for example, spontaneous abortion, fetal death, stillbirth, congenital anomalies, ectopic pregnancy) are considered SAEs.
- Pregnancy (maternal or paternal exposure to IP) does not meet the definition of an AE. However, to fulfill regulatory requirements, any pregnancy should be reported following the SAE process described in [Appendix 4](#) (Section 10.4) to collect data on the outcome for both mother and fetus.

8.3.6. Adverse Events of Special Interest

The sponsor CP or CRP will periodically review AESIs for this program, which include:

- bleeding/hemorrhagic events
- liver failure/liver injury
- hypertension
- proteinuria
- fistula
- GI perforation
- IRR (including hypersensitivity reactions)
- wound healing complications
- posterior reversible encephalopathy syndrome (PRES)
- ATEs
- venous thromboembolic events (VTEs)
- congestive heart failure

When appropriate, the sponsor CP or CRP will consult with the functionally independent Global Patient Safety therapeutic area physician or clinical research scientist.

8.3.7. Product Complaints

A product complaint is any written, electronic, or oral communication that alleges deficiencies related to the identity, quality, durability, reliability, safety, effectiveness, or performance of a trial intervention.

Sponsor collects product complaints on IP and drug delivery systems used in clinical studies in order to ensure the safety of study participants, monitor quality, and to facilitate process and product improvements.

Participants will be instructed to contact the investigator as soon as possible if he or she has a complaint or problem with the IP so that the situation can be assessed.

NOTE: AEs/SAEs that are associated with a product complaint will also follow the processes outlined in Section 8.3.3 and [Appendix 3](#) (Section 10.3) of the protocol.

8.3.7.1. Time Period for Detecting Product Complaints

- Product complaints that result in an AE will be detected, documented, and reported to the sponsor during all periods of the study in which the drug is used.
- If the investigator learns of any product complaint at any time after a participant has been discharged from the study, and such incident is considered reasonably related to a drug provided for the study, the investigator will promptly notify the sponsor.

8.3.7.2. Prompt Reporting of Product Complaints to Sponsor

- Product complaints will be reported to the sponsor using the Product Complaint Form within 24 hours after the investigator becomes aware of the complaint.
- The Product Complaint Form will be sent to the sponsor by the method provided in the form. If the primary method is unavailable, then an alternative method provided in the form should be utilized.

8.3.7.3. Follow-Up of Product Complaints

- Follow-up applies to all participants, including those who discontinue study intervention.
- The investigator is responsible for ensuring that follow-up includes any supplemental investigations as indicated to elucidate the nature and/or causality of the product complaint.
- New or updated information will be recorded on the originally completed form with all changes signed and dated by the investigator and submitted to the sponsor.

8.4. Treatment of Overdose

For this study, any dose of ramucirumab greater than a single dose of study intervention within a 24-hour time period will be considered an overdose.

The sponsor does not recommend specific treatment for an overdose. Participants should receive appropriate supportive care measures for AESIs or other AEs, as deemed necessary by the investigator.

In the event of an overdose, the investigator/treating physician should:

1. Contact the Medical Monitor immediately.
2. Closely monitor the participant for any AEs/SAEs and laboratory abnormalities until study intervention can no longer be detected systemically (at least 28 days).

Decisions regarding dose interruptions or modifications will be made by the investigator in consultation with the Medical Monitor based on the clinical evaluation of the participant.

8.5. Pharmacokinetics

- Whole blood samples will be collected for measurement of serum concentrations of ramucirumab as specified in the SoA (Section 1.3), Section 1.3.1, and Section 10.2.1.
- A maximum of 3 samples may be collected at additional time points during the study if warranted and agreed upon between the investigator and the sponsor. The timing of sampling may be altered during the course of the study based on newly available data (for example, to obtain data closer to the time of peak plasma concentrations) to ensure appropriate monitoring.
- Instructions for the collection and handling of biological samples will be provided by the sponsor. The actual date and time (24-hour clock time) of each sample will be recorded.

- Samples will be used to evaluate the PK of ramucirumab.
- Genetic analyses will not be performed on these serum samples. Participant confidentiality will be maintained.
- Pharmacokinetic samples will be retained for a maximum of 1 year following the last participant visit for the study. During this time, samples remaining after the bioanalyses may be used for exploratory analyses such as metabolism work, protein binding, and/or bioanalytical method cross-validation.

Drug concentration information that may unblind the study will not be reported to investigative sites or blinded personnel until the study has been unblinded.

8.5.1. Bioanalysis

Samples will be analyzed at a laboratory approved by the sponsor and stored at a facility designated by the sponsor.

Concentrations of ramucirumab will be assayed using a validated method. Analyses of samples collected from placebo treated participants are not planned.

Bioanalytical samples collected to measure investigational product concentrations will be retained for a maximum of 1 year following last participant visit for the study.

8.6. Pharmacodynamics

Pharmacodynamic parameters are not evaluated in this study.

8.7. Genetics

Genetics are not evaluated in this study.

A blood sample for deoxyribonucleic acid (DNA) isolation will be collected from participants.

See [Appendix 5](#) (Section 10.5) for information regarding genetic research and [Appendix 1](#) (Section 10.1.9) for details about sample retention and custody.

8.8. Biomarkers

Biomarkers are not evaluated in this study.

8.9. Immunogenicity Assessments

At the visits and times specified in the SoA (Section 1.3) and Section 1.3.1, venous blood samples will be collected to determine antibody production against ramucirumab. Antibodies may be further characterized for their ability to neutralize the activity of the ramucirumab. To interpret the results of immunogenicity, a venous blood sample will be collected at the same time points to determine the plasma concentrations of ramucirumab. All samples for immunogenicity should be taken predose when applicable and possible.

Additionally, blood samples for the determination of ramucirumab concentration and antiramucirumab antibodies are to be collected at the 30-day and 90-day follow-up visits (see SoA [Section 1.3]).

In the event of an IP-related IRR, see Section [6.1.1.2](#).

Antiramucirumab antibodies may be determined using a validated immunoassay at a laboratory designated by the sponsor or designee. Samples may be stored for a maximum of 15 years after the last participant visit for the trial, at a facility selected by the sponsor, to enable further analysis of immune responses to ramucirumab. The duration allows the sponsor to respond to regulatory requests related to the study drug.

Treatment-emergent antidrug antibodies (TE ADAs) are defined in Section [9.4.4](#).

The detection and characterization of antibodies to ramucirumab will be performed using a validated assay method at a laboratory under the supervision of the sponsor.

Refer to [Appendix 1](#) (Section [10.1.9](#)) for details on Sample Retention.

8.10. Health Economics

This section is not applicable for this study.

9. Statistical Considerations

9.1. Statistical Hypotheses

Formal statistical hypothesis testing is not planned. Therefore, adjustments for multiple testing do not apply.

9.2. Sample Size Determination

Approximately 60 participants will be enrolled and randomly assigned to study intervention (10 per group/dose level; 7 ramucirumab:3 placebo) to obtain at least 48 evaluable participants overall for an estimated total of at least 8 evaluable participants per intervention group (6 ramucirumab and at least 2 placebo). The sample size is not powered on the basis of statistical hypothesis testing. A participant will be considered evaluable when the participant completes up to 40 days of study procedures. When a participant does not complete up to 40 days of study procedures, the sponsor will be consulted if the participant will need to be replaced.

9.3. Populations for Analyses

The following populations are defined:

Population	Description
Entered	All participants who sign the ICF
Enrolled/Intent-to-Treat	All participants assigned to treatment, regardless of whether they take any doses of study treatment, or if they took the correct treatment. Participants will be analyzed according to the treatment group to which they were assigned.
Dose Evaluable	All participants who completed treatment
Safety	All participants randomly assigned to study intervention and who take at least 1 dose of study intervention. Participants will be analyzed according to the intervention they actually received.
Pharmacokinetic Analysis	All treated participants who received 1 dose of study intervention and have sufficient evaluable PK samples.

Abbreviations: ICF = informed consent form; PK = pharmacokinetic.

9.3.1. Study Participant Disposition

A detailed description of participant disposition will be provided at the end of the study.

9.3.2. Study Participant Characteristics

Demographic and baseline characteristics will be summarized by treatment group.

9.3.3. Treatment Compliance

No analyses of treatment compliance are planned.

9.4. Statistical Analyses

Statistical analysis of this study will be the responsibility of the sponsor or its designee. The primary analysis of the study will occur when there are at least 8 evaluable participants (6 ramucirumab:2 placebo) per intervention group.

Pharmacokinetic analyses will be conducted on data from all participants who receive 1 dose of IP and have evaluable PK.

Safety analyses will be conducted in the safety population.

Additional exploratory analyses of the data will be conducted as deemed appropriate. Study results may be pooled with the results of other studies for safety and population PK analysis purposes to avoid issues with post hoc analyses and incomplete disclosures of analyses.

Any change to the data analysis methods described in the protocol will require an amendment only if it changes a principal feature of the protocol. Any other change to the data analysis methods described in the protocol, and the justification for making the change, will be described in the statistical analysis plan (SAP) and the clinical study report (CSR). Additional exploratory analyses of the data will be conducted as deemed appropriate.

The SAP will be finalized prior to first participant, first visit, and it will include a more technical and detailed description of the statistical analyses described in this section. This section is a summary of the planned statistical analyses of the most important endpoints, including primary and key secondary endpoints.

9.4.1. Safety Analyses

9.4.1.1. Clinical Evaluation of Safety

All IP and protocol procedure AEs will be listed, and if the frequency of events allows, safety data will be summarized using descriptive methodology.

The incidence of AEs for each treatment will be presented by severity and by association with IP as perceived by the investigator. Adverse events reported to occur prior to study entry will be distinguished from those reported as new or increased in severity during the study. Each AE will be classified by the most suitable term from the medical regulatory dictionary.

All SAEs will be reported.

9.4.1.2. Statistical Evaluation of Safety

Safety parameters that will be assessed include safety laboratory parameters, vital sign measurements, and ECG parameters. The parameters will be listed, and summarized using standard descriptive statistics. Additional analysis will be performed if warranted upon review of the data.

9.4.2. Pharmacokinetic Analyses

9.4.2.1. Pharmacokinetic Parameter Estimation

Pharmacokinetic parameter estimates for ramucirumab will be calculated by standard noncompartmental methods of analysis.

The primary parameters for analysis will be t_{max} , C_{max} , and AUC of ramucirumab following IV and SC administration and bioavailability following SC administration. Other noncompartmental parameters, such as half-life, IV clearance, volume of distribution, apparent clearance, and volume of distribution following IV and SC ramucirumab administration may be reported.

In addition to noncompartmental analysis, non-linear mixed-effect modelling analysis of the Study JVDT PK data will be performed. This model will enable to estimate mean and variability (variance) of ramucirumab PK parameters following SC administration and to investigate potential covariate explaining that variability.

9.4.2.2. Pharmacokinetic Statistical Inference

Pharmacokinetic parameters will be evaluated to estimate ramucirumab AUC and C_{max} dose proportionality following SC administration in the dose range investigated. Log-transformed ramucirumab C_{max} and AUC parameters will be evaluated in a linear mixed-effects model with fixed effects for dose (Groups 1, 4, and 5 who received 350 mg will be combined). The treatment differences will be back-transformed to present the ratios of geometric means and the corresponding 90% confidence interval (CI).

For ramucirumab SC dosing PK parameters, the t_{max} will be analyzed using a Wilcoxon rank-sum test. Estimates of the median difference based on the observed medians, 90% CIs, and p-values from the Wilcoxon test will be calculated.

Ramucirumab bioavailability will be estimated (see Section 9.4.2.1).

Comparison of AUC and C_{max} between Group 1 and Group 4 will enable to assess the effect of changing the drug product concentration on the exposure. The log-transformed C_{max} and AUC will be the response variable, and the drug product concentration (that is, Group 1 and Group 4) is the explanatory variable.

Comparison of AUC and C_{max} between Group 1 and Group 5 will enable to assess the effect of changing the volume injected at one site of injection on the exposure. The log-transformed C_{max} and AUC will be the response variable, and the volume injected (that is, Group 1 and Group 5) is the explanatory variable.

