4.1. Overall Design

This is a single-site study in healthy participants who will receive a single dose of SC or IV ramucirumab. The study will be participant- and investigator-blinded, randomized, and placebo-controlled (7 ramucirumab:3 placebo per group/dose level). Placebo will be used as a comparator for both IV and SC to allow interpretation of safety and tolerability data following administration.

There will be sentinel dosing in this protocol; the initial 2 participants will be randomized/dosed (1 ramucirumab:1 placebo), and subsequently (the next day), the remaining participants in the group will be dosed. This will be subject to a satisfactory safety review by the investigator. This will occur on the first dose of SC (Group 1).

In Section 4.2, additional rationale is presented for the selection of healthy participants for this investigation.

Participants will be screened within 28 days prior to Day 1 of dosing for each group. Participants will be admitted to the CRU as part of an inpatient visit on Day -1 and will be sequentially enrolled. In each group, participants will be randomized to receive a single dose of IV or SC ramucirumab or placebo (7 ramucirumab:3 placebo per group).

There will be at least a 2-week safety observation period between the titrating SC injection groups (Groups 1 and 2), and between the SC and IV groups (Groups 2 and 3) while local laboratory data is reviewed by the sponsor and investigator. If the safety review is acceptable, Groups 4 and 5 may be dosed simultaneously to Group 3, as no dose escalation is occurring in those groups. Group 6 may be dosed with an infusion pump once the sponsor has reviewed both the safety and PK data (Groups 1 through 3) if the safety results are acceptable and if there is scientific value for investigating an additional group. The dose for Group 6 will be determined (maximum dose 350 mg). The plan for periodic reviews is presented Section 9.5.

The dose levels are provided below and may be adjusted based on safety reviews for preceding groups.

The participants receiving ramucirumab in each group will be administered the following dose level (up to 3 dose levels predicted to be ultimately used for therapeutic intent [see Section 4.3 for dose rationale]):

- **Group 1 will test a ramucirumab 350-mg SC dose**
 - administered at a concentration of 175 mg/mL as 1×2-mL injection.
- **Group 2 will test a ramucirumab 700-mg SC dose**

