 - administered at a concentration of 175 mg/mL as 2×2-mL injections.

- **Group 3 will test a ramucirumab IV dose (maximum of 350 mg)**
 - administered as a 60-minute infusion (maximum 35 mL×10 mg/mL).
 - Analysis of safety and PK data from Groups 1 to 3 will allow initiation of Group 6.
- **Group 4 will test a ramucirumab 350-mg SC dose**
 - administered at a concentration of 87.5 mg/mL as 2×2-mL injections
 - The purpose is to investigate the effect of a different drug product concentration on PK and safety and Group 1 will be the reference comparison group.
- **Group 5 will test a ramucirumab 350-mg SC dose**
 - administered at a concentration of 175 mg/mL as 2×1-mL injections
 - The purpose is to investigate the effect of a different volume administered at the injection site on PK and safety and Group 1 will be the reference comparison group.
- **Optional Group 6 may test SC ramucirumab dose, maximum 350 mg, to further understand SC ramucirumab PK and safety in healthy participants**
 - administered at a concentration of 175 mg/mL administered via an infusion pump according to the pharmacy manual.

The SC injection site will be the abdomen. See Section 6.1 for details.

Following the safety review of Groups 1 and 2, the sponsor and investigator agreed to allow doses to be reduced for remaining groups. This may mean that less groups may need to be studied. The asymptomatic transaminase increases observed during the safety review have also lead to a change in the exclusion criteria to further enhance safety of the participants. In view of these findings, subsequent doses will be capped at 350 mg. Lower doses may also be studied. These decisions will be based on emerging data (see Section 4.3 for further details).

Injection site pain (ISP) and ISRs will be monitored in each group, and a comparison of scorings will be used. The severity of ISP and ISRs reported across all participants will be evaluated. The data from Group 1, in comparison to Groups 4 and 5, will provide insight about the effect of injection volumes and ramucirumab concentration on ISP and ISR.

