limited number of personnel for consistency. The site of administration of each injection will be recorded; when there is more than 1 injection, the same site will not be used but another quadrant will be used.

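### Group 1 v 4 and Group 1 v 5 are labelled as concentration and volume effects, but both also change the number of injection sites and the mg per site

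*Protocol*

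**What the plan says.** Protocol 4.1 defines four SC injection groups, and SAP section 5 repeats them:

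- Group 1 (350 mg): "administered at a concentration of 175 mg/mL as 1×2-mL injection"
- Group 2 (700 mg): "administered at a concentration of 175 mg/mL as 2×2-mL injections"
- Group 4 (350 mg): "administered at a concentration of 87.5 mg/mL as 2×2-mL injections"
- Group 5 (350 mg): "administered at a concentration of 175 mg/mL as 2×1-mL injections"

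Two injections mean two anatomical sites. Protocol 6.1 says that for a second injection "the same site will not be used but another quadrant will be used".

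For Group 4, Protocol 4.1 states: "The purpose is to investigate the effect of a different drug product concentration on PK and safety". In Protocol 9.4.2.2 the Group 1 v 4 comparison of AUC and Cmax "will enable to assess the effect of changing the drug product concentration on the exposure", and the Group 1 v 5 comparison "will enable to assess the effect of changing the volume injected at one site of injection on the exposure". Concentration is the only explanatory variable named for the one, and volume the only one named for the other.

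SAP 9.3.2 keeps both labels and adds tmax. It then reads a PK difference among the three 350 mg SC groups as pointing to volume or to concentration, with no third explanation. On that basis it allows the dose-proportionality analysis to be repeated without one or two of those groups. By SAP section 3, the SAP supersedes the protocol's statistical section.

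The other planned SC comparisons are the dose-proportionality model and the tmax test, both with Groups 1, 4 and 5 combined (in the SAP model, if appropriate). The SAP's example code has dose as its only class variable and compares each level with control level 1. Neither document specifies Group 4 v 5, or a dose-normalised comparison of Group 2 with Group 4 or Group 5.

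**The concern.** A contrast can carry a single-factor label only if that factor alone differs between the groups. Here the reference group is the only SC injection group with one site, and both comparators have two. Any effect of dividing the dose between two quadrants would be credited to concentration in one contrast and to volume in the other.

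Two uses depend on the attribution. Protocol 2.1 says that these comparisons help to choose the dosing regimen and administration conditions for later development. SAP 9.3.2 uses them to decide which 350 mg groups stay in the dose-proportionality analysis. If the real cause of a difference were the number of sites, keeping Group 1 alone against Group 2 would mix dose with sites, whereas Groups 4 and 5 share Group 2's site count. Protocol 4.1 and SAP section 5 extend the same reading to injection site pain and reactions.

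**Working it through.** **1. Reproduce the stated doses.** Dose = sites × mL per site × mg/mL, with inputs from Protocol 4.1.

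| Group | Sites | mL per site | mg/mL | Total mL | mg per site | Dose (mg) |
|---|---|---|---|---|---|---|
| 1 | 1 | 2 | 175 | 2 | 350 | 350 |
| 2 | 2 | 2 | 175 | 4 | 350 | 700 |
| 4 | 2 | 2 | 87.5 | 4 | 175 | 350 |
| 5 | 2 | 1 | 175 | 2 | 175 | 350 |

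The doses match the plan. Because dose is the product of three factors, holding it at 350 mg while changing one factor forces another to change.

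**2. What each contrast changes.**

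| Contrast | Changes | Held fixed |
|---|---|---|
| 1 v 4 (planned) | concentration, sites, total volume, mg per site | volume per site, dose |
| 1 v 5 (planned) | volume per site, sites, mg per site | concentration, total volume, dose |
| 4 v 5 | concentration, volume per site, total volume | sites, mg per site, dose |
| 2 v 4 | concentration, mg per site, dose | sites, volume per site, total volume |
| 2 v 5 | volume per site, total volume, mg per site, dose | sites, concentration |
| 1 v 2 | sites, total volume, dose | volume per site, concentration, mg per site |

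**3. What each contrast estimates.** Let s, v and c be the changes in log dose-normalised exposure from doubling sites, volume per site and concentration. Take Group 1 as baseline m. Then Group 2 = m + s, Group 4 = m + s − c, and Group 5 = m + s − v.

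- Group 4 − Group 1 = s − c (labelled concentration)
- Group 5 − Group 1 = s − v (labelled volume)
- Group 4 − Group 5 = v − c (free of s)

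Groups 1, 4 and 5 give three means for four unknowns (m, s, v, c), so the factors cannot be separated. Adding Group 2 gives four equations: s = Group 2 − Group 1, c = Group 2 − Group 4, v = Group 2 − Group 5. This holds only under dose proportionality from 350 to 700 mg. If a departure d at 700 mg is allowed, those three differences become s + d, c + d and v + d. There are then five unknowns for four means, and separation is lost again.

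**4. Illustrations (all effect sizes assumed).**

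- Two sites multiply exposure by 1.10, 1.15 or 1.20, with no concentration or volume effect. Group 4/Group 1 and Group 5/Group 1 both equal 1.10, 1.15 or 1.20, while Group 4/Group 5 = 1.00.
- Doubling sites and doubling concentration each multiply exposure by 1.20. Group 4/Group 1 = 1.20/1.20 = 1.00, so a real concentration effect is hidden.
- Doubling volume and doubling concentration each multiply exposure by 1.20. Group 4/Group 5 = 1.20/1.20 = 1.00, so equal effects cancel.
- Dose-normalised exposure at 700 mg is 0.9, 1.1 or 1.2 times proportional, with no concentration effect. Group 4/Group 2 = 1/0.9 = 1.11, 1/1.1 = 0.91, or 1/1.2 = 0.83.

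**5. Precision.** Protocol 9.2 plans 6 evaluable ramucirumab participants per group. The 90% limits are the ratio multiplied and divided by exp(t × σ × √(2/6)), where t = 1.812 (10 df) and σ = √ln(1 + CV²). The documents give no CV for healthy participants. At an assumed CV of 20%, 30% or 40% the factor is 1.23, 1.36 or 1.50. For orientation, the 5th to 95th percentiles of the Appendix 6 SC simulation (350 mg twice weekly) imply ln(25.1/10.6)/3.29 = 0.262 for first-week AUC (CV 27%) and ln(227/87)/3.29 = 0.292 for Cmax (CV 30%). The added two-group contrasts have the same precision as the planned ones.

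**6. Eligibility.** Protocol 4.3 says that Groups 1 and 2 have already been enrolled, and 4.1 says that the exclusion criteria changed after their safety review. Contrasts of Group 1 or 2 with Group 4 or 5 cross that change. Group 4 v 5 does not.

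**The case against.** The strongest reply is that the design leaves no choice. At 350 mg, lowering the volume at one site without changing concentration means splitting the dose, so the Group 1 v 5 label is close to the practical question, and its wording refers to one site. The regimens are fully disclosed, and the SAP treatment names show them (1x2 mL, 2x2 mL, 2x1 mL). The documents promise insight into volume and concentration effects, not a clean separation. No hypothesis test is planned, and a ratio of 1.15 or 1.20 lies within the 90% limits computed above.

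Most of this stands, and it is why no redesign is asked for. It does not rescue the labels or the SAP sentence, which still name one factor where several differ. The covariate search in Protocol 9.4.2.1 names no covariate and the general allowance for exploratory work names no contrast, so neither corrects the attribution.

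A reader might go further and infer that adding Group 2 isolates each factor, or that Group 1 v 2 is a number-of-sites effect. The documents do not support this. Group 1 v 2 also doubles the dose, the dose-normalised contrasts assume proportionality, and Group 4 v 5 gives only concentration against volume. A reader might also infer that a site effect exists. Nothing in the documents shows one.

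**Conclusion.** The point holds as a matter of labelling and attribution. Neither planned contrast supports its single-factor label, and the SAP 9.3.2 sentence leaves out number of sites as an explanation. That follows from the stated regimens alone.

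The size of any misattribution is unknown: it equals whatever the site effect is, for which 1.10 to 1.20 is only an illustration. No sample-size figure is affected, and the planned ratios remain valid as comparisons between whole presentations. With about 6 active participants per group, the planned and added contrasts are descriptive and would not settle which factor is responsible.

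**What to change.** 1. In Protocol 9.4.2.2 and SAP 9.3.2, relabel Group 1 v 4 as a presentation effect (concentration plus number of sites) and Group 1 v 5 as a presentation effect (volume per site plus number of sites). Add number of sites to the SAP 9.3.2 attribution sentence.
2. Fit a model with group, not pooled dose, as the class variable, and report descriptive ratios with 90% CIs for:
   - Group 4 v 5, stating that it gives concentration against volume only and that equal effects cancel;
   - as supportive, dose-normalised Group 4 v 2 (concentration) and Group 5 v 2 (volume per site), stating that both assume dose proportionality from 350 to 700 mg.
3. Note that contrasts of Group 1 or 2 with Group 4 or 5 cross the change in exclusion criteria, and that Group 4 v 5 does not.
4. For injection site reactions and pain, show per-site results for Groups 1, 2, 4 and 5 side by side. The Schedule of Activities already has the questionnaire completed separately for each site. State that Group 4 v 2 also changes mg per site and total dose, and that Group 1 v 2 also changes total dose. Do not label Group 1 v 2 a number-of-sites effect.

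The cost is wording, one by-group model and a few extra table rows. It needs no new participants, samples or assessments.
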